The PI worked with an instructional designer, item writer, and media team to transition CHAT content, including 20 video clips of NH staff-resident interactions, to the online CHATO modules.³⁷ Scripts from the original CHAT were narrated to maintain content, integrating adult learning theories and principles for online learning, and eliminating a need for advanced literacy skills. Interactive scenario and game-based activities engage staff. For example, participants watch a video clip, select problem communication in the transcript, type their improved communication, and compare it to suggested corrections. Moderated online discussions are included in the modules that are supported on Training-Source.org, a free and publicly available learning portal.

IT functionality and content equivalency of the newly developed CHATO online modules was demonstrated by a convenient university-affiliated sample of nurses, CNAs, and students (N=9) with NH experience. They rated the online modules at 4.7 to 5.0 on a 1 to 5 scale (1 = strongly disagree to 5 = strongly agree) for increasing their knowledge, usefulness, clarity, and satisfaction. CHATO was rated as easy by 57%, while 43% found it somewhat challenging but not too difficult. All reported moderate to great improvement in recognizing and understanding ineffective communication and developing effective communication skills.³⁷ Pre to post test scores improved from $M = 82.4\%$ (SD 10.62) to $M = 91.21\%$ (SD 8.22). Effect sizes for pre-post changes for identifying ineffective, appropriate, and person-centered communication in a video clip were greater for CHATO participants compared to past CHAT participants (N = 217).^{34,37} Although the group testing CHATO may not represent all NH staff, findings confirm that CHATO is feasible and comparable in content and effects.

While CHAT effectively reduced RTC, the in-person classroom format required an onsite interventionist, which limits accessibility and feasibility for dissemination. A pilot test of

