acceptability and preliminary efficacy of online CHATO modules is the next logical step. The pilot will prepare for a pragmatic clinical trial that will test the effects of improved staff communication (from CHATO) on resident BPSD, using available clinical Minimum Data Set (MDS) data. Effects on psychotropic medication use, measured by MDS and Nursing Home Quality Measures (NHQM) data, will also be evaluated. This research will address the gap in rigorous trials testing nonpharmacological interventions to decrease BPSD that also identify strategies to improve intervention dissemination.²⁷ The goal is to increase access to CHATO training, as a tool to reduce BPSD and inappropriate psychotropic medication use to improve dementia care.

3 **STUDY DESIGN**

The R61 will prepare for the R01 pragmatic trial by establishing feasibility of online modules and preliminary efficacy of CHATO with NH staff. The research design is a randomized clinical trial. One NH will provide initial feasibility testing. Any modifications to the modules will be made. Then 6 nursing homes (estimated N=150 staff) will be randomly assigned to intervention or wait-list control groups. The primary outcome will be knowledge gain for staff completing CHATO training. Additional outcomes include resident quality measures related to behavioral and psychological symptoms of dementia (BPSD) on both resident and facility levels and facility level data related to inappropriate use of psychotropic medications to control BPSD.

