Staff Knowledge Gain. At time 1, nursing home staff in both groups will complete baseline pre-tests of knowledge and rating of communication. The immediate intervention group will then complete the online CHATO modules within a one-month period. This includes assessments of post-test knowledge, communication rating, program evaluation, and diffusion of innovation surveys at Time 2. Also, at Time 2, the wait-list control group will repeat the pre-tests of knowledge and communication rating and will then complete the CHATO online module training over a one-month period, followed by Time 3 collection of post-test knowledge, communication rating, program evaluation, and diffusion of innovation surveys. Knowledge gain and communication rating data will be compared between the intervention and wait-list control groups and within nursing homes before and after the CHATO training. Changes in knowledge from Time 1 (baseline) to Time 2 will be compared between immediate and wait-list groups using model estimates obtained with a linear mixed model (LMM) approach to account for repeated measures and clustering within nursing homes. Next, pre- to post-training changes in knowledge will be combined for immediate and wait-list groups and also tested using LMM approach. The models will be adjusted for covariates, such as staff role (RN, LPN, CNA, other), experience, and whether the nursing home has a SCU or not.

TABLE 1. R61 Study Design

Group	Time 1	1 Month	Time 2	1 Month	Time 3
Immediate 3 NHs	Baseline assessment ¹	CHATO training ²	Post-training assessment ³		
Wait list 3 NHs	Baseline assessment ¹		Repeat baseline assessment ¹	CHATO training ²	Post-training assessment ³

¹Pre-test knowledge, Communication rating; ² Three modules over a one-month period;

³ Post-test knowledge, Communication rating, Program Evaluation, Diffusion of Innovation

Resident Quality Measure Outcomes. In addition, nursing homes in both groups will provide monthly summary reports for behavioral symptom occurrence for the facility (in aggregate as well as for individual residents [deidentified]). A nursing home aggregate antipsychotic medication use report will also be collected and analyzed. The BPSD and medication reports will

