be provided for the one-month period before baseline data collection and for each month thereafter until the post-training assessment of the wait-listed nursing homes is completed (a total of seven months for both groups). Resident outcomes data will be compared between the intervention and wait-list control groups and within nursing homes before and after the CHATO training. Seven months of data will be plotted to examine changes in nursing homes and resident outcomes.

Implementation Strategies and Process Evaluation. An Implementation Toolkit for NHs and a CHATO Training Manual (See Appendices) have been created to provide support and implementation suggestions to pilot nursing homes. Several consultants provided feedback and additional resources to be included in these materials. Each NH will be given a three-month period to complete the CHATO training. One month for orientation, team development, and planning, one month to complete the three-week training, and one month for staff recognition and follow up. The CHATO Research Team will meet with the NH leadership at the beginning and end of this three-month period, manage CHATO training virtual discussion board, and provide technical assistance as necessary. The process evaluation includes an online implementation survey (See Appendices) which identifies the strategies NHs used to implement the training and includes the Artifacts of Culture survey. The survey uses the Diffusion of Innovation framework and mirrors the Implementation Toolkit. Additional process evaluation activities include: Leadership phone interviews completed by the consultants and external evaluators at LeadingAge and open-ended questions asked of direct care staff in the CHATO virtual discussion.

TABLE 2. R61 Research Timeline

	Quarter 1	Quarter 2	Quarter 3	Quarter 4	Quarter 5	Quarter 6
Planning (IRB, DSMB, Manuals, Measurement)						
Pilot CHATO Modules	—	—	—	—		
Analyses:		—	—	—		
Knowledge Gained			—	—		
Process Evaluation			—	—		
Resident Outcomes			—	—		
Dissemination			—	—	—	—

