5.2 Handling of Study Interventions

The study intervention is the Changing Talk Online (CHATO) training. The goal of course is to increase awareness of the importance of effective communication with older adults and to use evidence-based person-centered communication during interactions with older adults in nursing homes and other health care settings. The course is designed for staff in nursing homes, independent and assistive living, and health care settings in the community that include registered nurses, nursing assistants, nursing home dieticians, direct care professionals, other administrations and support employees. The total program is approximately 3 hours, split into 3 modules. Each module is approximately an hour, depending on the individual user. Upon completion of all three modules and 70% on a posttest, a certificate of completion (3 nursing contact hours) will be awarded.

Treatment 1: CHATO Training Module 1

This module contains information on the importance, benefits, and components of effective communication. This module covers the overarching goals and objectives, the benefits and components of effective communication, communication challenges of aging, and identification of effective communication (Videos).

Learning Outcomes

- Recognize the importance of communication to older adults.
- Identify barriers to communication in care of older adults.
- Distinguish between effective and ineffective communication strategies

Treatment 2: CHATO Training Module 2

This module contains information on common communication barriers and challenges, elderspeak communication, and effective and ineffective communication strategies. It reviews benefits and components of effective communication and introduces Elizabeth Layton paintings and thought exercises. The module also covers communication barriers and nursing home communication, ignoring talk vs. task talk vs. interpersonal talk, the Communication Predicament Model and elderspeak, and the identification of elderspeak and ineffective strategies (Videos).

Learning Outcomes

- Identify elderspeak and its potential negative messages.

- Contrast effective and ineffective communication strategies.
- Revise transcripts to reduce elderspeak and ineffective communication.

Treatment 3: CHATO Training Module 3

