6 STUDY PROCEDURES

6.1 Schedule of Pilot Evaluations in NHs

Assessment	Initial Leadership Meeting	Treatment CHATO Planning (1 st Month)	Treatment CHATO Training (2 nd Month)	Treatment CHATO Follow-up (3 rd Month)	Closing Leadership Meeting	Final Data Collection
NH Agreement	X					
Staff CHATO Participation		X				
Staff Demographics			X			
Staff CHATO Knowledge Pre-Test			X			
Communication Rating Sheet Pre-Test			X			
Staff CHATO Knowledge Post-Test			X			
Communication Rating Sheet Post-Test			X			
Modified Duke Diffusion of Innovation Intention Survey			X			
Staff CHATO Evaluation			X			
Implementation Survey				X		
The Artifacts of Culture Change Tool				X		
Staff Wage Data					X	
NH Level Resident Data						X
Leadership Phone Interviews						X

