10.2 Data Management

The participating nursing homes will not be responsible for collecting any data onsite. They will provide a NH Agreement, identify staff taking the training, take the Implementation Survey and The Artifacts of Culture Change Tool, and provide staff wage data. NH Chain Executives will provide NH level deidentified resident data.

Data will be collected in RedCAP and the Moodle learning system and provided to the data manager for data monitoring, cleaning, and analysis. Data will be stored on the collection platform and on secure servers at the University of Kansas Medical Center and/or the University of Iowa.

TABLE 5. Data Collection Forms Description

Data Collection Form	Description
NH Agreement	A signed letter of agreement from the participating NH indicating participation in the research.
Staff CHATO Participation	List of participating staff and their email address where they can receive the link to the CHATO training.
Staff Demographics	Participants' age, sex, race, ethnicity, NH employer, role, education, and length of time in current NH and health care role.
Staff CHATO Knowledge Pre-Test/Post-Test	Two forms (Forms A and B) measuring knowledge gained from training.
Communication Rating Sheet Pre-Test/Post-Test	Participant watches a video and answers questions which tests their ability to visually and audibly identify effective vs ineffective communication strategies and recognize elderspeak vs. person-centered care.
Modified Duke Diffusion of Innovation Intention Survey	Participants rates the training intervention on four scales: complexity and compatibility, observability/image, organizational support, and intention to use.
Staff CHATO Evaluation	Program evaluation of the CHATO training.
Implementation Survey	Measures approach, motivation, and incentives used to implement CHATO.
The Artifacts of Culture Change Tool	Measures NH care environment and practices, leadership and workplace practices, staffing outcomes, and occupancy.
Staff Wage Data	Wages per hour by NH role.
NH Level Resident Data	Resident behavioral and medication data.
Leadership Phone Interviews	Qualitative data regarding implementation strategies, lessons learned, and overall evaluation of the CHATO pilot from the NH leadership perspective.

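### The arms are assigned differently labelled knowledge tests at Time 2 and no form rule is stated, so form difficulty or same-form practice may be mixed with the training effect

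*Combined protocol and SAP*

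**What the plan says.** Section 3 (Study Design) names the primary outcome: "The primary outcome will be knowledge gain for staff completing CHATO training". Under Staff Knowledge Gain, both arms take the knowledge pre-test at Time 1. The immediate arm then trains, and "This includes assessments of post-test knowledge, communication rating, program evaluation, and diffusion of innovation surveys at Time 2". For the wait-list the text reads "Also, at Time 2, the wait-list control group will repeat the pre-tests of knowledge and communication rating", with training and the post-test following at Time 3. The footnotes to Table 1 agree: post-test knowledge for the immediate arm at Time 2, and the baseline assessment again for the wait-list.

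Section 10.2, Table 5, describes the knowledge pre-test and post-test in a single entry: "Two forms (Forms A and B) measuring knowledge gained from training". Nothing in the readable text says which form is used on which occasion, whether order is counterbalanced, or whether the forms were equated. Section 6.1 lists the "Staff CHATO Knowledge Pre-Test" and the post-test once each, in the training month, so it does not settle which form the wait-list takes when it repeats the test. Section 6.2.3 lists the tests without forms.

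Section 9.4 compares Time 1 to Time 2 change between arms with a linear mixed model, then combines the pre-to-post changes of both arms. The covariates it gives as examples are staff role, experience and special care unit. Test form is not among them.

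**The concern.** A difference in change between arms isolates training only if the measuring instrument behaves alike in both arms. Here the two arms are assigned differently labelled tests at the one time point where they are compared, and the test is known to exist in two versions. If the labels correspond to versions, everyone trained at Time 2 has taken one version and everyone untrained the other. No covariate can then separate form from training, and a larger sample does not help. The question has to be settled in the design.

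The analysis of combined pre-to-post changes is not a dependable substitute. Section 9.4 does not say whether the wait-list's untrained Time 1 to Time 2 change enters that model. If it does not, the analysis has no untrained comparator. At stake is the pilot's estimate of preliminary efficacy on its primary outcome. The readable text sets no decision threshold on knowledge.

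Two forms are described only for the knowledge test, so the point does not extend to the communication rating.

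**Working it through.** The plan gives no figure for form difference, retest gain or power, so there is nothing to reproduce. The check is to write down what each analysis estimates under each possible form rule.

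**Notation** (effects assumed additive): θ = training effect; d = expected untrained score on Form B minus Form A; p = gain from re-sitting the same form; q = gain on a second sitting with a new form; r = gain from re-sitting Form B at Time 3.

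**Randomised contrast, Time 1 to Time 2**

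| Form rule | Immediate | Wait-list | Contrast |
|---|---|---|---|
| 1. Pre-test = A, post-test = B | θ + d + q | p | θ + d + q − p |
| 2. Counterbalanced, wait-list re-sits own form | θ + q | p | θ + q − p |
| 3. Same rule in both arms (A then B shown) | θ + d + q | d + q | θ |

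If same-form gain is at least as large as new-form gain (p ≥ q), the practice part q − p is zero or negative. A net upward bias then needs d > p − q, that is, a sufficiently easier Form B.

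**Pooled pre-to-post change, equal arm weights, wait-list pre = Time 2**

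- Rule 1: immediate θ + d + q; wait-list θ + d + q − p (same q assumed at Time 3). Mean: θ + d + q − p/2.
- Fixed A-then-B in both arms, B again at Time 3: immediate θ + d + q; wait-list θ + r. Mean: θ + d/2 + (q + r)/2.

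So a fixed sequence clears the randomised contrast but leaves half the form difference, plus retest gain, in the pooled estimate.

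**Illustration of scale (assumed inputs)**

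The only knowledge scores in the documents are in section 2.2, from a "university-affiliated sample of nurses, CNAs, and students (N=9) with NH experience". They rose from 82.4 (SD 10.62) to 91.21 (SD 8.22), with forms not stated.

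- Gain: 91.21 − 82.4 = 8.81 points. Assumed net biases of 1, 2 and 3 points are 1/8.81 = 11%, 2/8.81 = 23% and 3/8.81 = 34% of it.
- With an assumed pre-post correlation of 0.5, SD of change = √(10.62² + 8.22² − 2 × 0.5 × 10.62 × 8.22) = 9.65.
- With 150 staff as 25 in each of 6 homes and an assumed ICC of change of 0.05, design effect = 1 + 24 × 0.05 = 2.2, and SE = 9.65 × √(2 × 2.2/75) = 2.34. For correlation 0.3 to 0.7 and ICC 0.01 to 0.10, the SE runs from 1.39 to 3.41.
- Chance of rejection when θ = 0 (noncentral t, 4 df, assumed two-sided 5% level):

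| Net bias | Mid-range | Range |
|---|---|---|
| 1 point | 6.3% | 5.6% to 8.7% |
| 2 points | 10.3% | 7.5% to 20.1% |
| 3 points | 17.0% | 10.6% to 38.1% |

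These are two-sided and apply to a bias of either sign. If the net bias is negative, nearly all the extra rejections point against training and are not false claims of benefit.

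**The case against.** The strongest reply is that nothing readable shows the arms using different forms. Pre-test and post-test may be labels for before and after training. Table 5 puts them in one entry, and if both arms simply re-sit one form, repeating the pre-test is literally true and the contrast is unbiased. A form drawn at random at each sitting, by the same rule in both arms, would also leave it unbiased. Section 3 says "An Implementation Toolkit for NHs and a CHATO Training Manual (See Appendices) have been created", but the appendices appear here as titles only, and a form rule may sit there or in the learning system. All of this stands, and it is why the point is conditional.

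A reader might infer that the trial is shown to be biased, or that the wording on repeating the pre-test forces a confounded comparison. The documents support neither. A reader might also take the rejection rates as the trial's false-positive risk. They rest wholly on assumed inputs and on SDs from nine people. At 1 point they are close to nominal, and practice alone would tend to lower the apparent effect. Additivity is itself doubtful when the earlier post-test mean was already 91.21%.

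What does not stand is treating this as mere missing detail. On the most natural reading of two labels and two forms, the stated procedure ties form to arm in the only randomised contrast of the primary outcome, and a cheap alternative avoids it.

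**Conclusion.** The point holds conditionally and should be fixed; confidence is medium. The differently labelled tests at Time 2, the two forms and the absence of a readable form rule are all in the text. That the pre-test is one form and the post-test the other is an inference. Under it, the randomised contrast carries a bias of d + q − p, which neither adjustment nor sample size removes. Under counterbalancing with the wait-list re-sitting its own form, the bias is q − p and tends to understate training. Under a common rule it is zero.

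Its size and sign cannot be determined from the documents. The consequence is limited to a pilot estimate of preliminary efficacy.

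**What to change.** In section 3, Table 1 and section 9.4, with matching edits in section 6.2.3 and Table 5 of section 10.2, replace the instruction that the wait-list repeats the pre-test with a rule that both arms use the same form sequence at Times 1 and 2. Preferably randomise staff within each nursing home to A-then-B or B-then-A, by the same rule in both arms, and fit form as a fixed effect. Name the wait-list's Time 3 form and state which score is its pre-training value.

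A fixed A-then-B sequence in both arms is an acceptable fallback for the randomised contrast only. With Form B again at Time 3, label the pooled pre-to-post estimate as still containing about half the form difference plus retest gain. Report it beside the wait-list's untrained Time 1 to Time 2 change. If the arms already share a sequence, one sentence saying so is enough.

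The costs are small: set-up in the learning system, access to the second form outside Module 3, and one model degree of freedom if form is fitted. No testing occasion is added. Untrained wait-list staff would see the second form before training and meet a form already seen at Time 3, so their own pre-to-post change carries some repeat-form practice. Section 5.2 also attaches a credential to the post-test: "Upon completion of all three modules and 70% on a posttest, a certificate of completion (3 nursing contact hours) will be awarded". The sponsor should confirm that either form, including one already seen, can serve that purpose.

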4 SELECTION AND ENROLLMENT OF PARTICIPANTS

4.1 Inclusion Criteria

NH Participating in CHATO. A NH home is eligible to participate in the study if they a) serve people with dementia, and b) have internet available for staff to complete the CHATO training, and c) are willing to complete leadership interviews and surveys. Seven NHs from Presbyterian Manor will participate in the pilot due to past relationships with organization. The nursing homes that were unable to participate in the original CHAT study will participate in the CHATO pilot.

Staff Participants. NH staff including CNAs and nurses who are permanent employees and who provide direct care at least 8 hours weekly will be invited to complete the CHATO training, available by URL link. Other personnel, such as housekeeping, dietary, and administrators may also participate. Our prior research found that a variety of staff benefit from CHAT, but we will focus on direct care nursing staff who communicate most with residents. Participation by as many staff as possible is desired to achieve facility-wide communication change. NHs will provide the staff that will take the training. Their roles and other demographics will be collected in the training module.

Resident Data. Aggregate, deidentified data for residents will be collected from participating NHs. Those with Alzheimer's disease or non-Alzheimer's dementia documented on the MDS

Active Diagnoses list will be included in the analyses.

